Title: Study 2 Learning New Words from Overhearing in Children with Autism Spectrum Disorder (ASD)

NCT Number: NCT05192109

Document date: 12/24/2024

The objective of this study was to see whether autistic and non-autistic children learn new words when they are presented via videoconferencing in one of two conditions: as part of speech directly addressed to the child (Addressed condition), as part of speech they overhear (Overheard condition). Children participated in the experimental task in both conditions (within-subject design). The method was a behavioral experiment in which children were exposed to a novel word (e.g., “toma”) in the context of one of three objects. The exposure either occurred with the experimenter looking directly at the child through the webcam (Addressed condition) or looking at another adult (Overheard condition). They were then shown the three objects and given a prompt to identify which object is labeled by the novel word (e.g., “where is the toma?”). Children’s eye gaze was coded as a measure of which object they preferred to look at after the prompt. After a delay of a few minutes, the test was repeated as a measure of retention.

The primary dependent variable reported here is the proportion of time children spend looking at the target object in each condition for each of the first test and the retention test. Track loss data points (that is, data points on which the child’s gaze could not be ascertained) are removed from analysis.

For each of the first test and the retention test, the primary statistical analysis involves asking whether children’s preference to look at the target is significantly greater in one condition than the other, and/or for one group or the other. Mixed-effects regression analyses are used with the proportion—empirical-logit transformed—of target looking as the dependent measure, participant as random effect, and condition and group and their interaction as fixed effects. If the interaction is significant, post-hoc testing using estimated marginal means is used.

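### The primary model has no term for the target word-object pair, so differences in target appeal can bias the condition effect (uneven assignment) or cost some power (balanced assignment)

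*Combined protocol and SAP*

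**What the plan says.** The Combined protocol and SAP has no numbered sections, so places are given by paragraph.

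- **First paragraph (method).** "Children participated in the experimental task in both conditions (within-subject design"), the conditions being Addressed and Overheard. In the task, "children were exposed to a novel word" "in the context of one of three objects", and were then shown all three objects and prompted for the named one. The test was repeated after a few minutes.
- **Second paragraph (dependent variable).** The outcome is the "proportion of time children spend looking at the target object in each condition for each of the first test and the retention test". No adjustment for prior liking of an object is described.
- **Third paragraph (primary analysis).** For each test, the question is whether children's "preference to look at the target is significantly greater in one condition than the other, and/or for one group or the other". The outcome is "empirical-logit transformed", and the mixed model has "participant as random effect, and condition and group and their interaction as fixed effects".

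The text does not give the number of word-object pairs, the number of trials per condition, how pairs were assigned to conditions or groups, the sample size, or any looking data.

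**The concern.** A word taught in one condition is no longer novel in the other, so a child who does both conditions needs at least two words, each with its own target. Looking at a target reflects learning, but also how attractive that object is beside the other two. The participant effect removes a child's overall tendency to look at targets. It does not remove a difference between that child's two targets.

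That difference therefore goes into the within-child contrast between conditions. What it does there depends on assignment, which the document does not describe. Uneven assignment shifts the estimate; balanced assignment leaves the difference in the residual. The condition effect and the condition-by-group interaction are both primary questions, at the first test and at the retention test. The group main effect is not exposed in this way if every child sees the same two pairs.

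**Working it through.** **Inputs.** From the document: two conditions within child, raw target looking on the empirical logit scale, and the model terms above. The document has no figure to reproduce. Assumed for illustration:

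- 60 children, 30 per group; two pairs; one trial per condition; both conditions observed for every child
- SD of the within-child condition difference 1.0 logit; two-sided 5% test
- pair difference d of 0.25 logit (looking shares of 0.42 v 0.36) or 0.5 logit (about 0.45 v 0.33)

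**Set-up.** For child i, the Addressed minus Overheard difference is D_i = B + s_i·d + e_i. B is the true condition effect, and s_i is +1 if the more appealing pair was in Addressed and -1 otherwise. The share with +1 is p. With one complete trial per condition, the mixed-model condition test is the test on D_i adjusted for group.

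**Bias without the pair term:** (2p-1)·d. For d = 0.5:

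- p = 0.5: 0 × 0.5 = 0
- p = 0.6: 0.2 × 0.5 = 0.10
- p = 0.8: 0.6 × 0.5 = 0.30
- p = 1: 1 × 0.5 = 0.50

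**False-positive rate for condition** (B = 0; simulation, 20,000 runs per setting):

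| p | No pair term, d = 0.25 / 0.5 | With pair term |
|---|---|---|
| 0.5 | 4% / 3% | 5% |
| 0.6 | 6% / 8% | 5% |
| 0.8 | 20% / 57% | 5% |
| 1 | 48% / 97% | not estimable |

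At p = 0.8 and d = 0.5, the rate without the term runs from about 22% (40 children, SD 1.5) to about 90% (80 children, SD 0.75).

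**Exact balance.** The estimate is unbiased and its true sampling variance does not change. The estimated variance is inflated by 1 + (d/SD)²:

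- SD 1.0: 1 + 0.25² = 1.06 and 1 + 0.5² = 1.25
- SD 2: 1 + 0.125² = 1.016 and 1 + 0.25² = 1.06

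Power for B = 0.4 at SD 1.0, d = 0.5, by hand: the true SE is 1/√60 = 0.129 and the reported SE is 0.129 × √1.25 = 0.144. The rejection threshold is about 2.00 × 0.144 = 0.289, against 2.00 × 0.129 = 0.258 with the pair term. Power is P(Z > (0.289 - 0.40)/0.129) = P(Z > -0.86), about 80%, against P(Z > -1.10), about 86%. At d = 0.25 it is 85% against 86%. At an SD of 2 the gain is only about 0.5 to 2 percentage points.

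**Interaction.** There are two separate routes to bias:

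1. *Assignment differs between groups.* Bias = 2d·(p_autistic - p_non-autistic). Shares of 0.7 and 0.3 with d = 0.5 give 2 × 0.5 × 0.4 = 0.40, with a false-positive rate of 26% without the pair and 5% with it. Shares of 0.6 and 0.5 give 0.10 and 4%.
2. *Assignment is uneven and appeal differs between groups.* Bias = (2p-1)·(d_autistic - d_non-autistic). With p = 0.8 in both groups and d of 0.5 and 0, this is 0.6 × 0.5 = 0.30. A pair main effect leaves it at 0.30 (false positives about 20% with or without the term). A pair-by-group term gives each group its own d, so the bias is zero whenever 0 < p < 1.

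**When the term can be fitted.** If each pair served one condition only, the pair column repeats the condition column: the design matrix has rank 4 for 5 columns, and no estimate exists.

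**The case against.** The strongest reply is that everything here is conditional. The document is a short account of a completed study, and silence about counterbalancing does not show that there was none. If targets were similar in appeal, d is near zero and nothing follows. With balanced assignment there is no bias and no excess of false positives, and the power gain is modest. With pairs fixed to conditions the term cannot be fitted, so the 48% / 97% rates are no argument for it. A large harm that the term repairs needs marked but incomplete imbalance, such as 80:20, for which the text gives no evidence.

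All of that stands, and it limits the strength of the point. It does not remove it. The model as written lacks the term, the term costs almost nothing under balance, and it protects the condition effect under any partial imbalance. Fitting it also requires looking up the assignment, which decides how the condition effect may be read.

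A reader might go further and infer that the targets were in fact confounded with condition, or that any observed condition effect is an object preference. The document supports neither reading. Nor may one infer that a pair main effect protects the interaction in general: it repairs only the first of the two routes.

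**Conclusion.** The point holds in conditional form. The primary model omits a likely source of within-child variation in its own outcome. The inference that each child had a different pair in each condition is strong but not stated in the document.

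What does not depend on assumed inputs is the structure: bias of (2p-1)d under uneven assignment, and a conservative test under balance when d is not zero. The sizes are illustrative only. Under the assumed inputs they run from a loss of about 1 to 6 power points with balance (0.5 to 2 at a difference SD of 2), through a false-positive rate of 6% / 8% at 60:40, to 20% / 57% at 80:20. More trials or more pairs would change these figures. This is an improvement that should be made, not evidence that the result is wrong; confidence is medium.

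**What to change.** 1. Where pairs cross conditions, add the target word-object pair as a fixed factor to the primary model at the first test and at the retention test. With many pairs, a crossed random intercept can replace it. The outcome and the post-hoc marginal means stay as stated.
2. Add pair by group as a check on the condition-by-group interaction.
3. State the number of pairs and how they were assigned, with pair counts by condition and group.
4. If each pair served only one condition, say that the condition effect cannot be separated from the targets used.
5. If results are already known, report the stated model and the pair-adjusted model side by side, and label the second as added afterwards.

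**Cost.** A model term, one further check and a few sentences. No new gaze coding is needed, because target looking cannot be scored without knowing the target. With two pairs the main effect uses one degree of freedom. Its variance factor for the condition effect, relative to balance, is 1/(1-(2p-1)²): 1.00, 1.04 and 1.56 at p = 0.5, 0.6 and 0.8. The standard error is therefore 1.00, 1.02 and 1.25 times as large.

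### The primary model has no term for where the target sat among the three objects, and its placement is not described; adding target location would be a cheap safeguard at both tests

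*Combined protocol and SAP*

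**What the plan says.** The Combined protocol and SAP has no numbered sections, so paragraphs are cited in order.

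- **First paragraph (method).** The task runs by videoconference, and every child does it in both the Addressed and the Overheard condition. At test, "They were then shown the three objects and given a prompt to identify which object is labeled by the novel word". The child's "eye gaze was coded as a measure of which object they preferred to look at after the prompt". The same test is given again some minutes later to measure retention.
- **Second paragraph (outcome).** The primary variable is the "proportion of time children spend looking at the target object in each condition for each of the first test and the retention test".
- **Third paragraph (analysis).** "Mixed-effects regression analyses are used with the proportion—empirical-logit transformed—of target looking as the dependent measure", with "participant as random effect, and condition and group and their interaction as fixed effects". This is done separately for the first test and the retention test.

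The document does not describe the layout of the three objects, how the target's place was assigned, or any balancing of that place over condition, group or test. It describes no looking measure from before the prompt. It gives no sample size, number of targets per child, alpha, power or SD.

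**The concern.** The outcome is the share of looking that falls on one of three objects. If children tend to look more at one place than another, that share depends partly on where the target sat, whether or not the word was learned. The analysis described has nothing that would remove such a preference: no location term, no baseline looking before the prompt and no stated balancing. The participant random effect absorbs what is constant within a child, but not a location effect that changes between that child's two conditions.

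At stake are the precision of the condition contrast and, if placement differed by condition or group, the validity of the corresponding contrast. If the retention test reuses the layout of the first test, any imbalance appears in both sets of results.

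**Working it through.** The plan has no figure to reproduce. Everything below is illustrative, and each input not in the document is marked as assumed. The ordinary logit stands in for the empirical logit.

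**Inputs**
- From the document: three objects; both conditions within child; logit-type outcome; no location term.
- Assumed: one target per child per condition; places equally likely and independent; shares of looking without learning of 0.45 centre and 0.275 each side, or more mildly 0.40 and 0.30; SD of a child's condition difference, apart from location, of 1.0 to 1.5 logits; two-sided alpha 0.05; 80% power when location is adjusted for.

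**1. Loss of precision under independent placement**

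Offset d = logit(centre) − logit(side). A target that is central one time in three has location variance d² × (1/3)(2/3) = d² × 2/9. The difference of two independent placements has twice that.

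| Centre share | d | Variance per test | Added to the difference |
|---|---|---|---|
| 0.45 | −0.201 − (−0.969) = 0.769 | 0.769² × 2/9 = 0.131 | 0.263 |
| 0.40 | −0.405 − (−0.847) = 0.442 | 0.442² × 2/9 = 0.043 | 0.087 |

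The variance ratio is R = 1 + added variance / SD². Power without the term is Φ(2.802/√R − 1.960), where 2.802 = 1.960 + 0.842.

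| Centre share | SD | R | Power without the term |
|---|---|---|---|
| 0.45 | 1.0 | 1.263 | 0.703 |
| 0.45 | 1.5 | 1.117 | 0.755 |
| 0.40 | 1.0 | 1.087 | 0.767 |
| 0.40 | 1.5 | 1.039 | 0.785 |

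**2. Bias when the spread differs between conditions**

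Bias = (share of central targets in Addressed − share in Overheard) × d. With 0.40 against 0.267 and d = 0.769, this is 0.133 × 0.769 = 0.10 logits. If the two shares are equal, the bias in the condition contrast is zero, however unevenly the places are used overall.

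**3. Simulation by assignment scheme**

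The simulation used the paired condition contrast without a location term, 10,000 runs per case. Further assumptions were one target per condition, residual SD 1.0 per observation (so 1.41 for the difference), 60 children, centre share 0.50 (d = 1.099) and a true effect of 0 or 0.5 logits.

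| Placement | Bias | True SE | Model SE | Type I error | Power |
|---|---|---|---|---|---|
| No position preference, random placement | 0.00 | 0.18 | 0.18 | 0.05 | 0.76 |
| Independent random | 0.00 | 0.21 | 0.21 | 0.05 | 0.66 |
| Same place in both conditions | 0.00 | 0.19 | 0.18 | 0.05 | 0.77 |
| Exactly balanced, differing within child | 0.00 | 0.18 | 0.22 | 0.02 | 0.64 |
| Central in 50% v 25% | 0.27 | 0.20 | 0.21 | 0.25 | not comparable (biased) |

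At a centre share of 0.40, independent placement gives power 0.75, and the 50% v 25% case gives type I error 0.09.

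Exact balance protects the estimate, but if places differ within child the unadjusted model counts location variation as error and its SE is too large. If a child's two targets share a place, an additive location effect drops out of the condition contrast. It then remains as between-child variation, which affects the group contrast.

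**The case against.** The strongest reply is that the document reports no position preference, and without one nothing changes. Target place may also have been balanced by design; in a one-page summary, silence about this may be only a gap in reporting. Both points stand, and they are why the size is conditional.

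Three stronger inferences are tempting, and the text does not support them:

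- **That location bias is actually distorting the results.** This needs both a position preference and an assignment scheme that lets it through. The document shows neither and rules out neither.
- **That uneven use of the three places is enough to bias the condition contrast.** It is not. The spread must differ between conditions, or between groups for the group contrast.
- **That gaze is coded less accurately at some positions.** The document mentions the webcam only for the experimenter's gaze and says nothing about coding accuracy by position.

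The remedy also has limits. A location factor cannot be separated from condition if layouts were fixed by condition. It has no role if the target was always in one place. As an additive term, it does not deal with a position preference that differs between groups. The document is written in the past tense, so changing the primary model now may be post hoc.

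What survives is that the model lists no location term, that nothing else described would remove a position preference, and that even exact balance can leave the unadjusted SE too large.

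**Conclusion.** The point holds as a low-cost improvement and does not show that the analysis is wrong. Under the assumptions in the working, a plausible position preference takes power from 80% to 77–79% (centre share 0.40) or 70–76% (0.45). More targets per condition shrink the loss. It disappears for the condition contrast if a child's target sits in the same place in both conditions, or if there is no preference. Bias arises only where placement differs between the conditions or groups being compared: about 0.10 logits in the 40% v 27% example. None of these sizes can be fixed from the document, so confidence in the magnitude is low, and a reader should not conclude that the condition or group results are biased.

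**What to change.** 1. State how the target's place was assigned, and tabulate it by condition, group and test.
2. Add target location (three levels) as a fixed factor in the mixed model at both the first and the retention test, provided it is not collinear with condition. If it is collinear, say so and report the limitation, because no covariate can then separate the two.
3. If results have already been seen, keep the planned model as primary and report the location-adjusted model beside it as a labelled sensitivity analysis.

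No new data should be needed, since scoring a look as a target look already requires knowing where the target was. The cost is two degrees of freedom per model, with no gain if there is no position preference. A table showing the same spread of places across conditions and groups would settle the question of bias from an additive location effect; adjustment could then still improve precision.

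### The participant random effect cannot represent a negative correlation between a child's two condition scores; if that correlation is negative, the condition and interaction tests are too liberal

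*Combined protocol and SAP*

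**What the plan says.** The document has no numbered sections. Its first paragraph describes a within-subject design in which each child is tested in both conditions. The second paragraph defines the primary outcome as "the proportion of time children spend looking at the target object in each condition for each of the first test and the retention test". The third paragraph gives the model: "Mixed-effects regression analyses are used with the proportion—empirical-logit transformed—of target looking as the dependent measure", with "participant as random effect, and condition and group and their interaction as fixed effects". The first test and the retention test are analysed separately. The aim is to see whether target looking is "significantly greater in one condition than the other, and/or for one group or the other". The interaction then acts as a gate: "If the interaction is significant, post-hoc testing using estimated marginal means is used".

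No other within-child covariance is named. Nothing is said about a participant variance estimated at zero, the degrees-of-freedom method, the significance level, the sample size, the number of trials or where the target appears on the screen.

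**The concern.** On the natural reading, each model holds two values per child and a random intercept. A random intercept sets the covariance of those two values equal to the between-child variance, and a variance cannot fall below zero. When the data show a negative covariance, the fitted variance is zero and the model treats a child's two scores as independent.

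A negative covariance is possible in a three-object looking task. A child drawn to one screen place scores high when the target is there and low when it is elsewhere. If the target place differs between that child's two conditions, the preference pushes the two scores apart.

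The condition comparison, the interaction that opens the post-hoc tests, and the within-group condition contrasts would then have p-values that are too small. The group main effect would err the other way.

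**Working it through.** **Inputs.** From the document: two conditions per child, two groups, a participant random effect, and a separate model for each test. Assumed because the document is silent: one score per child per condition, complete pairs, equal variances, equal groups of 15, 20 or 30, two-sided 0.05, and a correlation rho between the two scores over a range. The plan states no figure to reproduce.

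**Closed form.** Let N be the total number of children and sigma^2 the variance of one score. The within-child mean square MSW estimates sigma^2(1 - rho), and the between-child mean square MSB estimates sigma^2(1 + rho).

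- If MSB is at least MSW, the REML fit uses MSW as the error for condition and interaction. This is the paired analysis.
- If MSB is below MSW, the participant variance is set to zero and the error becomes the pooled value (SSB + SSW)/(2(N - 2)), which estimates sigma^2.

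The true variance of a child's condition difference is 2 sigma^2(1 - rho). With the participant variance at zero, the model uses 2 sigma^2. For negative rho the large-sample ratio of model to true standard error is therefore 1/sqrt(1 - rho), and the type I error is 2(1 - Phi(1.96/sqrt(1 - rho))). At rho = -0.2 the ratio is 1/sqrt(1.2) = 0.913, and 1.96 x 0.913 = 1.79, which gives 7.4%. The same ratio applies to the interaction. For rho of zero or above the ratio is 1.

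**Finite samples.** Null data were simulated from this closed form, with N - 2 degrees of freedom when the participant variance is positive and 2(N - 2) when it is zero. Results for 40 children:

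| rho | SE ratio, large sample | Type I, large sample | Type I, simulated | Chance that the participant variance is set to zero |
|---|---|---|---|---|
| -0.5 | 0.816 | 11.0% | 10.9% | 100% |
| -0.3 | 0.877 | 8.6% | 8.5% | 97% |
| -0.2 | 0.913 | 7.4% | 7.4% | 89% |
| -0.1 | 0.953 | 6.2% | 6.5% | 73% |
| 0 | 1.000 | 5.0% | 5.7% | 50% |
| +0.1 | 1.000 | 5.0% | 5.3% | 27% |
| +0.2 | 1.000 | 5.0% | 5.1% | 11% |
| +0.3 | 1.000 | 5.0% | 5.0% | 3% |

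Totals of 30 and 60 children agree to within about 0.3 points. Using N - 2 degrees of freedom throughout lowers the figures somewhat (7.0% at -0.2 and 8.1% at -0.3 with 40 children) but does not remove the excess. An analysis of each child's condition difference stays at about 5% in every row.

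**Zero correlation.** The excess at rho = 0 is a boundary effect: about half of data sets have a negative sample covariance, which is cut to zero. It shrinks from 6.0% with 20 children to 5.3% with 200.

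**Group effect.** At rho = -0.3 the group standard error is about 1.20 times its true value. At rho = -0.2 the group test rejects in 2.6 to 2.9% of null data sets.

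**Group contrasts within one condition.** Their standard error rests on the total variance. That is (MSB + MSW)/2 whether or not the participant variance is set to zero, so it is not affected.

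**The case against.** The strongest reply is that nothing in the document shows a negative correlation, and that a participant random intercept is a conventional choice for this design. Four parts of that reply stand.

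- **Zero is not a failure.** A reader might infer that the error bars are already wrong when a child's two scores are uncorrelated. They are not: the model can represent zero, and only the small boundary effect remains.
- **The place-preference argument depends on target placement, which is not stated.** Suppose 30 to 50% of children strongly favour one place. Simulated correlations are about -0.11 to -0.36, depending on the assumed strength of the preference, if the target place must differ between conditions. They are about +0.01 if the place is drawn independently, and +0.42 to +0.75 if it is the same in both.
- **Stable differences between children push the other way.** If a share w of the variance is common to a child's two scores and the rest has correlation -r, the total is zero at w = r/(1 + r). For r = 0.11 and 0.19 this is 0.11/1.11 = 10% and 0.19/1.19 = 16%. A modest common component cancels the weaker place effects.
- **Zero-variance fits need not be common.** A reader might expect them routinely with two values per child. They are frequent only when rho is near zero or negative, as the table shows, and that is the open question.

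The two-score reading is also an inference. If several trials or time bins per condition entered the model, the missing by-participant condition slope would be a separate matter and these figures would not apply.

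The reply does not show that the correlation is positive. The document gives no basis for assuming that either.

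**Conclusion.** The point holds as a conditional weakness. If the correlation between a child's Addressed and Overheard scores is negative, the condition, interaction and within-group condition tests are too liberal: about 6 to 6.6% at -0.1, 7.3% at -0.2 and 8.5% at -0.3. The group main effect is then too conservative. At zero the excess is small, and from about +0.2 upward it is immaterial.

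These sizes rest on 15 to 30 children per group, complete pairs, equal variances, two-sided 0.05 and one score per child per condition, all of which are assumed. The document does not support a reading that the reported p-values are in fact too small, or that error rates near 11% are to be expected: that rate needs a correlation near -0.5, which nothing in the text suggests. The reason to act is that the protection costs almost nothing.

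**What to change.** At each test, keep the fixed effects and replace the bounded participant random effect with a compound-symmetry within-child covariance whose correlation may be negative. Use Satterthwaite or Kenward-Roger degrees of freedom, and take the estimated-marginal-means contrasts from that model. With complete pairs this is equivalent to testing each child's Addressed-minus-Overheard difference (its mean for condition, its group difference for interaction) and each child's mean for group. Children with one usable condition are still kept.

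The cost is one line of wording and a rerun of two models. The document is written in the past tense, so the change should be disclosed as such. With complete pairs, results are unchanged when the estimated correlation is positive. When it is negative, condition and interaction p-values become slightly less favourable.

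An unstructured 2x2 covariance is also valid, but a reader should not assume that it leaves everything else alone. It gives each condition its own variance, so group contrasts within a condition can change even when the correlation is positive. In one simulated complete data set with 20 children per group, their standard errors were 0.46 and 0.64, against 0.56 for both under the planned structure.
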